## 8. ADVERSE EVENTS

### 8.1 Definitions

#### 8.1.1 Adverse Event Definition

Adverse event (AE) means any untoward medical occurrence in a patient or subject administered a pharmaceutical product; the untoward medical occurrence does not necessarily have a causal relationship with this treatment. An AE can therefore be any unfavorable and unintended sign (including an abnormal laboratory finding), symptom, or disease temporally associated with the use of a medicinal (investigational) product whether or not it is related to the medicinal product. This includes any newly occurring event, or a previous condition that has increased in severity or frequency since the administration of study drug.

An abnormal laboratory value will not be assessed as an AE unless that value leads to discontinuation or delay in treatment, dose modification, therapeutic intervention, or is considered by the investigator to be a clinically significant change from baseline.

The investigator (or physician designee) is responsible for verifying and providing source documentation for all adverse events and assigning the attribution for all adverse events for subjects enrolled.

For the purposes of this clinical study, AEs include events which are either new or represent detectable exacerbations of pre-existing conditions.

The term “disease progression” should not be reported as an adverse event term; instead, signs and symptoms of clinical sequelae resulting from disease progression/lack of efficacy will be reported if they fulfill the serious adverse event definition. As an example, "worsening of underlying disease" or the clinical diagnosis that is associated with disease progression should be reported.

Adverse events may include, but are not limited to:

- Subjective or objective symptoms provided by the patient and/or observed by the Investigator or study staff including laboratory abnormalities of clinical significance.
- Any AEs experienced by the patient from the time of informed consent through the completion of final study procedures (approximately 30 days following the last dose of study drug).
- AEs not previously observed in the patient that emerge during the protocol-specified AE reporting period, including signs or symptoms associated with the underlying disease that were not present before the AE reporting period

- Complications that occur as a result of protocol-mandated interventions (e.g., invasive procedures such as biopsies).

The following are NOT considered AEs:

- Pre-existing condition: A pre-existing condition (documented on the medical history CRF) is not considered an AE unless the severity, frequency, or character of the event worsens during the study period.
- Pre-planned or elective hospitalization: A hospitalization planned before signing the informed consent form is not considered an SAE, but rather a therapeutic intervention. However, if during the pre-planned hospitalization an event occurs, which prolongs the hospitalization or meets any other SAE criteria, the event will be considered an SAE. Surgeries or interventions that were under consideration, but not performed before enrollment in the study, will not be considered serious if they are performed after enrollment in the study for a condition that has not changed from its baseline level. Elective hospitalizations for social reasons, solely for the administration of chemotherapy, or due to long travel distances are also not SAEs.
- Diagnostic testing and procedures: Testing and procedures should not to be reported as AEs or SAEs, but rather the cause for the test or procedure should be reported.
- Asymptomatic treatment related lymphocytosis: This event should also not be considered an AE. Patients with treatment-related lymphocytosis should remain on study treatment and continue with all study-related procedures.

---

Recommended Adverse Event Recording Guidelines

---

Attribution	Grade 1	Grade 2	Grade 3	Grade 4	Grade 5
Unrelated	Phase I	Phase I	Phase I	Phase I	Phase I
			Phase II	Phase II	Phase II
				Phase III	Phase III
Unlikely	Phase I	Phase I	Phase I	Phase I	Phase I
			Phase II	Phase II	Phase II
				Phase III	Phase III
Possible	Phase I	Phase I	Phase I	Phase I	Phase I
	Phase II	Phase II	Phase II	Phase II	Phase II
		Phase III	Phase III	Phase III	Phase III
Probable	Phase I	Phase I	Phase I	Phase I	Phase I
	Phase II	Phase II	Phase II	Phase II	Phase II
		Phase III	Phase III	Phase III	Phase III
Definitive	Phase I	Phase I	Phase I	Phase I	Phase I
	Phase II	Phase II	Phase II	Phase II	Phase II
		Phase III	Phase III	Phase III	Phase III

---

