### 7.1.6 Efficacy Analysis

Overall response and complete response at each of the pre-specified time points will be described as percentage with exact ninety-five percent (95%) confidence interval based on binomial distribution. PFS and OS curves will be described using Kaplan-Meier methods. The curves will be presented with 95% confidence intervals. Patients who are still on follow-up without experiencing the relevant event by the closeout date will be censored. The maximum grade of each toxicity will be described in tabular form as count and percentages.

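### Section 8.1.1 makes reporting of progression-related symptoms depend on seriousness, while its own AE bullet and Phase II recording table do not, so non-serious Grade 3-4 events ascribed to lymphoma have no settled rule

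*Combined protocol and SAP*

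**What the plan says.** Section 8.1.1 defines an adverse event without regard to cause: "the untoward medical occurrence does not necessarily have a causal relationship with this treatment". It then bars progression as an AE term and says instead that "signs and symptoms of clinical sequelae resulting from disease progression/lack of efficacy will be reported if they fulfill the serious adverse event definition". Its next sentence gives, as an example of what to report, a worsening of the underlying disease, or says that "the clinical diagnosis that is associated with disease progression should be reported".

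Further down, an illustrative list of adverse events includes those newly emerging in the reporting period, "including signs or symptoms associated with the underlying disease that were not present before the AE reporting period". The section closes with a grid titled "Recommended Adverse Event Recording Guidelines". Its Phase II entries cover Grades 3, 4 and 5 for Unrelated and Unlikely events, and Grades 1 to 5 for Possible, Probable and Definitive events. It has no column for seriousness.

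The investigator or a physician designee is responsible for "assigning the attribution for all adverse events for subjects enrolled". On the analysis side, section 7.1.6 says: "The maximum grade of each toxicity will be described in tabular form as count and percentages". It does not say whether toxicity means all events or only treatment-related ones.

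**The concern.** The same event can be handled in two ways by staff who each follow the protocol. A non-serious Grade 3 or 4 symptom that the investigator puts down to lymphoma may go unrecorded under the progression sentence, while the bullet and the grid call for it to be recorded.

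The trial is open-label and single-arm (4.1, 6.12), so no control group separates drug effect from disease. Marrow-only disease is eligible (5.1, criterion 3), and section 6.4.2 says both drugs can cause cytopenias and a related infection risk, so disease and treatment can produce the same clinical picture. If the event is recorded with its attribution, the judgement can be revisited. If it is omitted because of the attribution, it cannot. The direction of any error is known: reported severe toxicity can only go down.

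The example in the paragraph adds a smaller problem. It excludes progression as a term and then invites a near-synonym, which would put an efficacy outcome into the safety data under another name.

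**Working it through.** The plan gives no figure on this point to reproduce, so the check is mainly a comparison of rules.

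**Step 1: can the event exist?** Take an event within the collection window (8.1.1: consent to about 30 days after the last dose), Grade 3 or 4, not serious, ascribed to lymphoma. Section 8.1.3 defines seriousness by outcome (death, immediate threat to life, hospitalization, incapacity, birth defect), plus important medical events on judgement. It does not use grade. A non-serious Grade 3-4 event is therefore possible.

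**Step 2: apply each rule to it.**

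| Rule | Seriousness condition | Attribution or grade condition | Result |
|---|---|---|---|
| 8.1.1, progression sentence | yes | applies to sequelae of progression or lack of efficacy | may be left out |
| 8.1.1, general definition | none | none | AE |
| 8.1.1, bullet on underlying disease | none | new in the reporting period | AE |
| 8.1.1, recording grid, Phase II | none | Unrelated or Unlikely: Grade 3-5 only | recorded |
| 8.2, opening paragraph | none | clinically relevant laboratory deterioration or other clinical finding | AE |

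**Step 3: look for precedence.** Nothing in 7.1.6, 7.1.8, 8.1.1 or 8.2 says which rule governs when they disagree.

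**Step 4: narrow the gap.** Section 8.1.1 already makes a laboratory value an AE when it leads to delay, dose modification, intervention or discontinuation, or is judged a clinically significant change. Table 6-2 ties low neutrophil and platelet counts to holding or reducing ixazomib, so such counts qualify whatever their cause. The gap therefore mainly concerns other signs, symptoms and diagnoses.

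**Step 5: scale.** With n = 24 (7.1.1), one omitted patient changes a row by 1/24 = 4.2 percentage points, provided the omitted event was that patient's only Grade 3-4 occurrence of that toxicity. As an illustration, with exact 95% limits (lower: 0.025 quantile of Beta(x, n−x+1); upper: 0.975 quantile of Beta(x+1, n−x)):

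- x = 3: 3/24 = 12.5%, interval 2.7% to 32.4%
- x = 2: 2/24 = 8.3%, interval 1.0% to 27.0%

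The counts 3 and 2 are chosen only to show the effect of one omission. The document gives no basis for predicting how many events would be affected.

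**The case against.** The best defence is that the sentence concerns reporting, the word section 8.2 uses for SAEs sent to the company's safety unit, while the grid concerns recording. On that view nothing is lost. The sentence also says if, not only if, and the next sentence asks for the associated diagnosis without repeating the condition. The bullet belongs to an illustrative list, and the grid is only recommended.

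Part of this stands: the text is ambiguous, and the three provisions differ in force. But the sentence sits in the AE definition and begins with what may be used as an AE term, while SAE reporting has its own section. The seriousness condition does no work unless non-serious sequelae are treated differently. The ambiguity is itself a reason to reconcile the text.

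Several stronger readings are tempting, and the document does not support them:

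- *That 7.1.6 is the only summary of harm.* Section 7.1.8 plans a safety analysis of all dosed subjects and monitors Grade 3 or higher peripheral neuropathy. That stopping rule carries no attribution condition.
- *That the grid records every event.* Unrelated and Unlikely Grade 1-2 events have no Phase II entry.
- *That disease-related cytopenias generally disappear.* Step 4 shows that many are AEs already.
- *That half the cohort, 12 of 24, could be exposed, from the 50% early-progression rate in 7.1.9.* At that rate the plan's own figure is an 89.6% chance of stopping after 10 patients, so a full cohort is unlikely. Early progression there is also defined by tumour measurement or new lesions, not by symptoms.

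**Conclusion.** The contradiction is real, both within the text of 8.1.1 and between that text and its recording grid. It leaves non-serious Grade 3-4 events ascribed to lymphoma without a settled rule. This rests on reading the progression sentence as serious-only, which is the natural reading but not the only possible one.

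The total loss cannot be computed; the scale is 4.2 percentage points per omitted patient per toxicity row. The effect is limited to the AE collection window and mainly to events other than laboratory changes that already qualify as AEs. No effect on the primary endpoint or on the neuropathy stopping rule is shown. The point is worth correcting because the possible bias runs in one direction, a single-arm trial has no internal comparison to reveal it, and the remedy is short.

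One dependency matters. If toxicity in 7.1.6 means treatment-related events only, events ascribed to lymphoma leave the table even after 8.1.1 is corrected. Both sections need the change.

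**What to change.** In 8.1.1, delete the seriousness condition attached to sequelae of progression, and delete the example that reports a worsening of the underlying disease. State that progression is an efficacy outcome under any name and is not an AE term. State that its signs, symptoms and diagnoses are recorded under their own terms, with grade, attribution and seriousness, by the existing Phase II grid: all Grade 3-5 events whatever the attribution or seriousness, and Grade 1-2 events as the grid already provides.

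In 7.1.6, state that the toxicity table is all-cause, with treatment-related events shown as a subset.

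The cost is one rewritten paragraph and one added sentence, a few more AE entries, and slightly higher reported rates. No new procedures are needed, and the SAE reporting rules in 8.2 stay as they are.

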## **4. STUDY DESIGN**

### **4.1 Overview of Study Design**

Open label, single center, single –arm, phase II testing the combination of ixazomib and rituximab in the treatment of subjects with relapsed or refractory MCL. The study will enroll 24 patients. The treatment plan starts with oral ixazomib at the US approved dose of 4 mg. All subjects will have disease restaging at 8 weeks. Rituximab IV will be given once weekly for the first 4 weeks. Rituximab IV will restart at cycle 3, and continue monthly until cycle 12.

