## 5.2 Exclusion Criteria

Patients meeting any of the following exclusion criteria are not to be enrolled in the study:

1. Female patients who are lactating or have a positive serum pregnancy test during the screening period.
2. Failure to have fully recovered (i.e.,  $\leq$  Grade 1 toxicity) from the reversible effects of prior chemotherapy.
3. Major surgery within 14 days before enrollment.

4. Radiotherapy within 14 days before enrollment. If the involved field is small, 7 days will be considered a sufficient interval between treatment and administration of the ixazomib.
5. Central nervous system involvement.
6. Infection requiring systemic antibiotic therapy or other serious infection within 14 days before study enrollment. Patient may be eligible, if infectious disease specialist approves start of therapy AND subject has completed course of antibiotic therapy.
7. Evidence of current uncontrolled cardiovascular conditions, including uncontrolled hypertension, uncontrolled cardiac arrhythmias, symptomatic congestive heart failure, unstable angina, or myocardial infarction within the past 6 months.
8. Systemic treatment, within 14 days before the first dose of ixazomib, with strong CYP3A inducers (rifampin, rifapentine, rifabutin, carbamazepine, phenytoin, phenobarbital), or use of St. John's wort.
9. Ongoing or active systemic infection, active (DNA PCR positivity) hepatitis B or C virus infection, or known human immunodeficiency virus (HIV) positive.
10. Any serious medical or psychiatric illness that could, in the investigator's opinion, potentially interfere with the completion of treatment according to this protocol.
11. Known allergy to any of the study medications, their analogues, or excipients in the various formulations of any agent.
12. Known GI disease or GI procedure that could interfere with the oral absorption or tolerance of ixazomib including difficulty swallowing.
13. Diagnosed or treated for another malignancy within 2 years before study enrollment or previously diagnosed with another malignancy and have any evidence of residual disease. Patients with nonmelanoma skin cancer or carcinoma in situ of any type are not excluded if they have undergone complete resection.
14. Patient has  $\geq$  Grade 3 peripheral neuropathy, or Grade 2 with pain on clinical examination during the screening period.

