Once ixazomib is reduced for any toxicity, the dose may not be re-escalated.

Rituximab and Ixazomib individually are FDA approved for NHL and multiple myeloma, respectively. The combination of a proteasome inhibitor plus anti-CD20 antibody has been studied previously.

Mechanistically, rituximab and Ixazomib does not have overlapping mechanism of action. We have in place Hepatitis screening at baseline. Rituximab does not have overlapping non-hematologic toxicity with Ixazomib. However, they will both cause cytotoxicity to hematopoietic cells, cytopenias and related increased risk for infection. We are mainly concerned for non-hematologic toxicities. Therefore, we would like to monitor peripheral neuropathy toxicities. We will stop the current dose level and consider treating patients at a lower dose level for Ixazomib if we observe at anytime that the rate of any grade of peripheral neuropathy toxicity is > 40% or the rate of grade 3 or higher peripheral neuropathy toxicity is >10%.

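### The any-grade neuropathy rule can run on an undercount, because the phase II recording table omits low-grade events judged unrelated or unlikely

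*Combined protocol and SAP*

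**What the plan says.** Section 4.1 describes a single-arm, open-label "phase II testing the combination of ixazomib and rituximab", and states: "The study will enroll 24 patients".

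The table in Section 8.1.1 headed "Recommended Adverse Event Recording Guidelines" lists phase II trials by attribution and grade. Unrelated and unlikely events appear from Grade 3 upward. Possible, probable and definitive events appear at every grade.

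In Section 6.4, the text after Table 6-3 names peripheral neuropathy as the toxicity to watch. It says the current dose level will be stopped and a lower one considered "if we observe at anytime that the rate of any grade of peripheral neuropathy toxicity is > 40" per cent, or if "the rate of grade 3 or higher peripheral neuropathy toxicity is >10" per cent. It gives no attribution, observation window, minimum number of patients or data source.

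Section 7.1.6 adds: "The maximum grade of each toxicity will be described in tabular form as count and percentages". This too has no attribution limit. Nothing in the documents exempts neuropathy from the recording table.

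On who may enter, exclusion criterion 14 bars Grade 3 or worse neuropathy, "or Grade 2 with pain on clinical examination during the screening period". Grade 1 and painless Grade 2 neuropathy are therefore not barred by that criterion.

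**The concern.** A rule on any-grade neuropathy depends mostly on how Grade 1 and 2 events are captured, and those are the grades that the recording table filters by attribution. Every patient has had at least two prior lines of therapy, and some may enter with low-grade neuropathy. Section 8.1.1 makes worsening of an existing condition an adverse event. If the investigator judges a low-grade worsening unlikely to be related, however, the table does not call for it to be recorded.

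Two things follow if the rule and the tabulation are fed from recorded events. The neuropathy count depends on a causality judgement made without blinding and without a control arm. The error also runs one way: events can be missing from the count but not added to it, so the regimen can look only safer than it is. At stake are the sensitivity of one stated safety trigger and the completeness of the low-grade neuropathy rows in the toxicity table.

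**Working it through.** **Which rules the table can touch.** The plan gives operating characteristics only for the Grade 3 or higher rule in 7.1.8, so that was reproduced first. With prior Beta(0.2, 0.8), the posterior after x events in n patients is Beta(0.2 + x, 0.8 + n − x). Stopping requires P(p > 0.20) > 0.90.

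- n = 6: 0.927 at 3 events, 0.721 at 2.
- n = 12: 0.943 at 5 events, 0.829 at 4.
- n = 18: 0.959 at 7 events, 0.888 at 6.

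The printed boundaries of 3, 5 and 7 are correct. Exact enumeration with looks at 6, 12 and 18 also matches all seven printed stopping probabilities and average sample sizes. For example, at a true rate of 0.20 it gives 0.1439 and 21.76. The recording table keeps Grade 3 to 5 events under every attribution for phase II, so these figures do not move. Only the any-grade rule and the low-grade tabulation are exposed.

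**Inputs for the any-grade rule.** From the documents: a maximum of 24 patients, a trigger at a rate above 40%, checked at any time. Assumed, because the documents give no value:

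- p, the true share of patients with any-grade neuropathy;
- u, the share of affected patients whose only neuropathy is Grade 1 or 2 and judged unrelated or unlikely, and so unrecorded.

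Patients are treated as independent. The recorded rate is q = p(1 − u).

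**Trigger counts.** The smallest counts above 40% are 3 of 6, 5 of 12, 8 of 18 and 10 of 24.

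**Formulas.**

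- Single look at 24 patients: P(X ≥ 10), with X ~ Binomial(24, q).
- Repeated looks: let f(n, s) be the probability of s events in n patients without having crossed. Then f(n, s) = (1 − q) f(n − 1, s) + q f(n − 1, s − 1). At each look, the probability with s > 0.4n is removed and added to the probability of crossing.

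**Results: chance of exceeding 40% by patient 24.**

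| p | u | q | Looks at 6, 12, 18, 24 | After every patient | Single look at 24 |
|---|---|---|---|---|---|
| 50% | 0% | 0.500 | 92% | 97% | 85% |
| 50% | 15% | 0.425 | 78% | 90% | 61% |
| 50% | 25% | 0.375 | 64% | 82% | 41% |
| 45% | 0% | 0.450 | 84% | 93% | 70% |
| 45% | 15% | 0.3825 | 66% | 84% | 44% |
| 45% | 25% | 0.3375 | 52% | 75% | 27% |

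At p = 50%, moving from full recording to 25% unrecorded costs 92 − 64 = 28 points with four looks and 97 − 82 = 15 points with a check after every patient. A single look would give 85 − 41 = 44 points.

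The check after every patient loses least because one event in the first two patients already exceeds 40%. The chance of that is 1 − (1 − q)², which is 75% at q = 0.500 and 61% at q = 0.375. Section 6.4 sets no minimum number of patients, so this reading cannot be ruled out.

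**Shift in the effective threshold.** The recorded rate reaches 40% when the true rate is 0.40/(1 − u): 0.40/0.85 = 47% for u = 15%, and 0.40/0.75 = 53% for u = 25%.

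**The case against.** The strongest reply is that no undercount has been shown. The recording guidelines are only recommended. Section 8.1.1 also makes the investigator responsible for source documentation and attribution of all adverse events, and the Section 6.4 rule acts on what is observed, in one centre with 24 patients. This stands as far as it goes: a reader might infer that the rule does run on an undercount, but the documents support only that it can. They do not say the rule is run from source, and Section 9.1 places study data in two databases.

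Second, toxicity may mean drug-related neuropathy. The rule follows Table 6-3, which is introduced as covering events related to ixazomib, under a heading about treatment-associated toxicity. On that reading all relevant grades are recorded and nothing is lost against the definition. This is a fair reading, but Section 6.4 does not state it, and the count would still depend on an unblinded causality call.

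Third, the attribution route is narrower than exclusion 14 alone suggests. Exclusion 2 requires recovery to Grade 1 or less from reversible effects of prior chemotherapy, and exclusion 16 bars prior proteasome inhibitors. This makes attribution to earlier therapy less likely without closing the route.

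Three further readings are tempting and should not be drawn. The 7.1.8 boundaries are not weakened, as shown above. The tolerability measure in 7.1.3 is completion at set weeks, and the recording table removes no completion data. The 44-point loss belongs to a single look at 24 patients, whereas Section 6.4 says the rate is watched at any time.

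**Conclusion.** The concern holds as a gap between two passages. The recording table does not call for Grade 1 and 2 neuropathy judged unrelated or unlikely, while the Section 6.4 rule and the Section 7.1.6 tabulation cover every grade without an attribution limit. If recorded events feed them, the result can be biased downward and cannot be biased upward by this route.

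The size is illustrative. At an assumed true rate of 50% and 25% of affected patients unrecorded, the chance that the rule is ever triggered falls by about 15 to 28 points, depending on how often the rate is checked. With nothing unrecorded the loss is zero. Both the rate and the share are assumptions, and the look schedule is not stated. A clarification is worth making because neuropathy is the toxicity that the protocol singles out for monitoring.

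**What to change.** Add to Section 8.1.1: *All new or worsening peripheral neuropathy is recorded at every grade with its attribution, whatever that attribution is.* In the toxicity tables, present neuropathy both overall and by attribution.

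Reconcile the Section 6.4 rule with the Section 8.1.1 table. The sponsor should state whether the any-grade rule counts all treatment-emergent neuropathy or only related events, and from which data source the count is taken. With every event and its attribution recorded, either count can be produced. No change to the threshold, the dose or Section 7.1.8 is proposed.

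The cost is a few more adverse event entries for one term in 24 patients. The reported low-grade neuropathy rate may rise.
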